6 STUDY OBJECTIVES AND RATIONALE

6.1 STUDY OBJECTIVES

Primary:

- To determine the safety and tolerability of AT -10 compared to Clopidogrel administered orally to humans.
- To compare effect of AT -10 (loading and maintenance doses) Vs approved doses of Clopidogrel (loading and maintenance doses) on platelet aggregation in poor and extensive metabolizers.
- To confirm the AT -10 loading dose (PD equivalent dose to the Clopidogrel 300 mg) and the AT -10 maintenance dose (PD equivalent to the Clopidogrel 75 mg) given as a loading dose followed by 5 days of maintenance dose

Secondary:

• To determine the single and multiple dose pharmacokinetics (PK) of Clopidogrel, AT -10, and active metabolite MP-H4.

6.2 RATIONALE

Requirement of conducting this study:

The growing body of literature implicating CYP2C19 loss-of-function alleles in adverse clopidogrel responses prompted the USFDA to ask the application holder to implement a boxed warning on the clopidogrel package insert stating, "Effectiveness of Clopidogrel bisulfate depends on conversion to an active metabolite by the cytochrome P450 (CYP) system, principally CYP2C19. Consider use of another platelet P2Y₁₂ inhibitor in patients identified as CYP2C19 poor metabolizers". Hence there is a well-established relationship exist between CYP2C19 deficient pharmacogenomic populations and drug response, that results in diminished effectiveness in poor metabolizers.

To overcome the limitations of clopidogrel associated with CYP2C19 metabolism, Ipca has developed AT-10, a prodrug that is metabolically converted, in one CYP-dependent step, to produce the active metabolite of the approved listed drug Plavix (clopidogrel bisulfate tablet, 300 mg; NDA 20839). A major advantage of the pro-drug AT-10 is its more efficient metabolism through one CYP-dependent step, as compared to the two-step process for clopidogrel involving several CYP450 isoenzymes. It is possible that AT-10 may provide a faster and more consistent inhibition of platelet function, thereby producing important clinical benefits for patients. The response to AT-10 may not be influenced by genetic CYP2C19 polymorphisms to the extent of its influence in clopidogrel, thus eliminating the need for characterization of clopidogrel responsiveness and thereby maintaining effectiveness in all patients, including those patients who are identified as CYP2C19 poor metabolizers as well. So in order to explore the PK-PD and safety profile of AT-10 in Indian population the current study has been proposed.

CONFIDENTIAL

Page 32 of 74

Ipca Laboratories Ltd Version 1.0 (Amendment 3.0)

Selection of AT-10 doses for this study:

It is important to note that AT-10 is an intermediate metabolite in the metabolic pathway of Clopidogrel to the active metabolite. Therefore, this study does not represent the first exposure of AT-10 in humans. It does, however, represent the first direct administration of AT-10 to humans. The highest single dose planned for AT-10 is 40 mg and the highest single dose planned for Clopidogrel is 300 mg.

Further, in the nonclinical toxicology studies in primates conducted by Ipca, the no adverse effect level has been determined to be 150 mg/kg (48 mg/kg human equivalent dose) resulting in a 72-fold safety margin for the AT-10 40 mg dose.

The PD potency of AT-10 was thought to be between 4 and 10 times greater than that of Clopidogrel. This was based on the nonclinical studies that have been completed and the amount of AT-10 exposure that results from a dose of Clopidogrel. Specifically, in a rodent model, PD indicated that AT-10 is approximately 10 times more potent than Clopidogrel. In a primate model, the PK exposure observed with AT-10 was approximately 4 times higher than that observed with Clopidogrel when adjusted for dose. Further, when the metabolic fate of Clopidogrel is assessed, it is estimated that approximately 8 – 10% of the administered dose of Clopidogrel is metabolized into AT-10. Based on these data, the effective loading dose of AT-10 was expected to be between 30 and 75 mg and the effective maintenance dose was expected to be between 7.5 and 20 mg.

Further, the 40 mg loading dose and 10 mg maintenance doses of AT-10 for this study has been selected based on a pharmacodynamically similar dose to the clopidogrel 300-mg loading dose and the clopidogrel 75-mg maintenance dose. This dose was determined from our earlier conducted study entitled "A Phase 1, Randomized, Single-Ascending and Multiple-Dose Safety, Tolerability, Pharmacokinetic, and Pharmacodynamic Study of AT 10 in Healthy Subjects Considered Extensive Metabolizers of CYP2C19 Based on Genotyping." (*1/*1 alleles) (Protocol Number IPCA AT-10 2012-001).

Selection of duration of therapy:

As per PIL of Plavix, dose-dependent inhibition of platelet aggregation can be seen 2 hours after single oral doses of Plavix. Repeated doses of 75 mg Plavix per day inhibit ADP-induced platelet aggregation on the first day, and inhibition reaches steady state between Day 3 and Day 7. At steady state, the average inhibition level observed with a dose of 75 mg Plavix per day was between 40% and 60%. Platelet aggregation and bleeding time gradually return to baseline values after treatment is discontinued, generally in about 5 days.

Further, since AT 10 (2-oxo-clopidogrel) is one of the metabolite in the biotransformation pathway of clopidogrel that leads to the active metabolite MPH4, it is anticipated that multiple dose study that includes a single loading dose of AT-10 followed by five (5) daily doses of the maintenance dose of AT-10 compared to the approved loading and maintenance doses of Plavix® (Clopidogrel) would be sufficient as the steady state is being reached by Day 6.

CONFIDENTIAL

Page 33 of 74

Ipca Laboratories Ltd Version 1.0 (Amendment 3.0)

Rational for study population:

As significant amount (>35%) of Indian population either lacks CYP2C19 enzyme or have reducedfunction genes which may results in lower response to Clopidogrel when administered at recommended dose. (Umamaheswaran G, et al.2014) there exists a need of drug(s) which required less degree of metabolism by CYP2C19 enzyme but still gives a desired therapeutic action at lower dose covering entire population (poor as well as extensive metabolizers). Hence, we feel that further evaluation of AT-10 in Indian population is worth exploring.

Ipca Laboratories Ltd Version 1.0 (Amendment 3.0)

7 STUDY DESIGN

7.1 Design

This study is an open label, two-period, crossover study wherein each subject will receive a single loading dose followed by 5 daily doses (maintenance dose) of either AT-10 or Clopidogrel in Period 1 and then crossover to receive the other therapy (AT -10 or Clopidogrel) in Period 2.

40 subjects are planned to be randomized into the study. Out of this, 20 subjects would be extensive CYP2C19 metabolizers and 20 would be poor CYP2C19 metabolizers. The 20 extensive metabolizers will be randomized on a 1:1 basis into Groups 1 and 3. The 20 poor metabolizers will be randomized on a 1:1 basis into Groups 2 and 4. Subjects who withdraw or are removed from the study will not be replaced.

The dosing scheme is as follows:

Group & Sequence	Period 1	Period 2	
Group 1	AT -10 40mg on Day 1	Clopidogrel 300 mg on Day 1	
(n=10, extensive metabolizers)	AT -10 10 mg on Days, 2, 3, 4, 5 & 6	Clopidogrel 75 mg on Days 2, 3, 4, 5 & 6	
Sequence 1			
Group 2	AT -10 40 mg on Day 1	Clopidogrel 300 mg on Day 1	
(n=10, poor metabolizers)	AT -10 10 mg on Days, 2, 3, 4, 5,	Clopidogrel 75 mg on Days 2, 3,	
Sequence 1	& 6	4, 5 & 6	
Group 3	Clopidogrel 300 mg on Day 1	AT -10 40 mg on Day 1	
(n=10, extensive metabolizers)	Clopidogrel 75 mg on Days 2, 3, 4, 5, & 6	AT -10 10 mg on Days 2, 3, 4, 5 & 6	
Sequence 2			
Group 4	Clopidogrel 300 mg on Day 1	AT -10 40 mg on Day 1	
(n=10, poor metabolizers)	Clopidogrel 75 mg on Days 2, 3, 4,	AT -10 10 mg on Days 2, 3, 4, 5	
Sequence 2	5, & 6	& 6	

8 POPULATION / SAMPLE SIZE

This is the first administration of AT-10 in Indian population. The sample size chosen is not based on a statistical calculation of PD effect or PK variability, but rather on the number of subjects deemed necessary to assess the safety and tolerability of AT-10 in humans, establish the PK parameters of AT-10 in humans, and to generate proof-of-concept data (evaluate the set objectives) on the pharmacodynamic effect of AT-10.

40 Healthy male and / or female subjects of ages 18-45 years (both ages inclusive) will be enrolled in the study.

- o Group 1: n=10, Healthy male and / or female subjects who are extensive (normal) metabolizers
- o Group 2: n=10, Healthy male and / or female subjects who are poor metabolizers
- o Group 3: n=10, Healthy male and / or female subjects who are extensive (normal) metabolizers
- Group 4: n=10, Healthy male and / or female subjects who are poor metabolizers

The site will carry out general screening with CYP2C19 based genotyping, so that site will have database of volunteers in sufficient number who are extensive (normal) metabolizers and poor metabolizers.

8.1 ENTRY CRITERIA

8.1.1 Inclusion Criteria

Subjects will be considered eligible for the study based on the following criteria:

- 1) Subjects who are willing to provide voluntary informed consent and are willing to participate in the study.
- 2) Normal healthy human adult male and/or female subjects between 18-45 years (both ages inclusive) of age.
- 3) Body Mass Index of 18.50 to 29.90 kg/m² (both inclusive).
- 4) No evidence of underlying disease during the pre-study screening, medical history, clinical examination and laboratory investigations performed within 28 days prior to commencement of the study.
- 5) Subject classified as extensive (normal) metabolizer (*1/*1) or poor metabolizer (*2/*2, *2/*3, *3/*3) based on CYP2C19 allele 1 and 2, 3 and 17 genotyping.
- 6) Pre-study screening laboratory tests are either normal or within acceptable limits or are considered by the Investigator to be of no clinical significance with respect to participation in the study.
- 7) Negative test results for alcohol, drugs of abuse, Beta hCG test (for female subjects only) and who is negative or non-reactive for antibodies to HIV 1 and 2, hepatitis B & C and RPR at the time of screening.
- 8) 12-lead ECG recording within normal or within acceptable limits or as considered by the Investigator to be of no clinical significance with respect to his/her participation in the study.
- 9) Normal chest X-ray taken within 6 month of enrollment.

CONFIDENTIAL

Page 36 of 74

Ipca Laboratories Ltd Version 1.0 (Amendment 3.0)

- 10) Subjects who are available for the entire study period and are capable of understanding and communicating with the investigators and clinical study facility staff.
- 11) Subject must agree to use an acceptable method of contraception at least 48.00 hours prior to dosing of IP, during the study & for 07 days after study completion.

8.1.2 Exclusion Criteria

Subjects will be excluded from the study based on the following criteria:

- 1) Known allergic to Clopidogrel, AT-10 or any component of the formulation and to any other related class of drug.
- History or presence of significant cardiovascular, respiratory, hepatic, renal, hematological, gastrointestinal, endocrine, immunologic, dermatologic, musculoskeletal, neurological or psychiatric disease.
- 3) Female subjects who are nursing mothers\lactating women.
- 4) History/presence of significant alcohol dependence (abuse) or drug abuse within the past 1 year.
- 5) History of chronic smoking (more than 10 units per day of cigarettes, bidis, or any other form) or chronic consumption of tobacco products.
- 6) History/presence of significant Asthma, urticaria or other allergic type reactions after taking any medication.
- 7) History/presence of clinically significant illness within 04 weeks before the start of the study.
- 8) History of clinically relevant allergy (except for untreated, asymptomatic, seasonal allergies at time of dosing) or any allergic reactions to any drugs.
- 9) History of vascular collapse.
- 10) Subjects scheduled for surgery any time during study or within 07 days after study completion.
- 11) History of difficulty in donating blood.
- 12) Subjects who have unsuitable veins for repeated vein puncture.
- 13) Subjects who have donated blood or loss of blood 50 ml to 100 ml within 30 days or 101 ml to 200 ml within 60 days or > 200 ml within 90 days (excluding volume drawn at screening for this study) prior to first dose of study medication.
- 14) Subjects who have received a known investigational drug within ten elimination half-life of the administered drug prior to first dose of study medication or who have participated in a clinical drug study or bioequivalence study within 90 days prior to the first dose of study medication, whichever is greater; or subjects who have not completed sufficient days of no participation in clinical study as indicated by the investigator / institute of the last study participation as reflected in OVIS.
- 15) Subjects who have taken prescription medication or OTC products (including vitamins and natural products) within 14 days prior to dosing of IP, including topical medication.
- 16) Use of any medication known to alter hepatic enzyme activity within 28 days prior to the initial dose of study medication (e.g. Omeprazole or other proton pump inhibitors).
- 17) Reported or documented use of aspirin or its derivatives, including patches, creams, rubs, sprays, or non-steroidal anti-inflammatory drug(s) within the last 14 days.
- 18) Subject who was hospitalized within 28 days prior to administration of the study medication.
- 19) History of difficulty in swallowing.

CONFIDENTIAL

Page 37 of 74

- 20) Subjects with known increased risks of bleeding (eg, frequent nose bleeding, recent trauma, surgery or other pathological condition), including known history of bleeding dyscrasias such as Von Willebrand, Hemophilia A or B, or any other type of bleeding disorder.
- 21) Any abnormal laboratory value or physical finding which may interfere with the interpretation of test results or cause a health hazard for the volunteer if he / she participates in the study.
- 22) Evidence of skin lesions on forearm or signs of vein puncture on the forearm suggestive of recent donation or participation in clinical trial.
- 23) Platelet count outside the normal range at screening or housing for Period 1.
- 24) Subject has a condition the Investigator believes would interfere with the ability to provide informed consent or comply with study instructions, or that might confound the interpretation of the study results or put the subject at undue risk.

8.2 DISCONTINUATION AND WITHDRAWAL CRITERIA

- Subjects are free to withdraw from the study at any time without stating any reason.
- The investigator can withdraw a subject from the particular period or from the study if:
 - 1. The subject suffers from significant inter current illness or undergoes surgery during the study.
 - 2. The subject experiences an AE, when withdrawal would be in the best interest of the subject or subject experiences SAE will be withdrawn from the study unconditionally.
 - 3. The subject fails to comply with the requirements of the protocol.
 - 4. The subject tests positive for alcohol and/or drugs of abuse during the time of study period.
 - 5. The subject is found positive for Pregnancy test or becomes pregnant during the study.
 - 6. It is necessary to further protect the health of the subject or the integrity of the study.
 - 7. Any subject cross participates in other clinical study.
 - 8. The subject is found to hide important medical history which in opinion of Principal Investigator may compromise study objectives or his/her safety during participation in this study
 - 9. In Principal Investigator's opinion it is not in the subject's best interest to continue or any other justifiable reason, which should be adequately documented.

10. Sometimes, though rarely, the sponsor may stop the study.

Note:

- 1) No additional subjects will be enrolled to replace dropouts
- 2) Any subject who vomits within 2 hours after administration of study drug, the PK blood sampling for that period will be stopped and PK data will not be evaluated for PK; however, the pharmacodynamic assessments should be conducted. Vomiting early after administration of the test medication may decrease the bioavailability of the test drug. However, the subject may continue with subsequent periods (if any) of the study.
- 3) The final report will include reasons for withdrawal.
- 4) If any subject is withdrawn or dropped-out, subject's shall be requested for end of study safety assessment to ensure subject's safety. Subject withdrawal during the study shall be handled as per applicable SOPs with adequate documentation.

CONFIDENTIAL

Page 38 of 74

Ipca Laboratories Ltd Version 1.0 (Amendment 3.0)

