Clopidogrel is extensively metabolized by two main metabolic pathways: one mediated by esterases and leading to hydrolysis into an inactive carboxylic acid derivative (85% of circulating metabolites) and one mediated by multiple cytochrome P450 enzymes. Cytochromes first oxidize clopidogrel to a 2-oxo-clopidogrel intermediate metabolite. Subsequent metabolism of the 2-oxo-clopidogrel intermediate metabolite is formed mostly by CYP2C19 with contributions from several other CYP enzymes, including CYP1A2, CYP2B6 and CYP3A. The active thiol metabolite binds rapidly and irreversibly to platelet receptors, thus inhibiting platelet aggregation for the lifespan of the platelet.

The Cmax of the active metabolite is twice as high following a single 300 mg clopidogrel loading dose as it is after four days of 75 mg maintenance dose. Cmax occurs approximately 30 to 60 minutes after dosing. In the 75 to 300 mg dose range, the pharmacokinetics of the active metabolite deviates from dose proportionality: 4-fold the dose results in 2.0-fold and 2.7-fold the Cmax and AUC, respectively.

Elimination

Following an oral dose of 14C-labeled clopidogrel in humans, approximately 50% of total radioactivity was excreted in urine and approximately 46% in feces over the 5 days post dosing. After a single, oral dose of 75 mg, clopidogrel has a half-life of approximately 6 hours. The half-life of the active metabolite is about 30 minutes.

Drug Interactions:

Effect of other drugs on Plavix

Clopidogrel is metabolized to its active metabolite in part by CYP2C19.

CYP2C19 inducers

Since clopidogrel is metabolized to its active metabolite partly by CYP2C19, use of drugs that induce the activity of this enzyme would be expected to result in increased drug levels of the active metabolite of clopidogrel.

Rifampin strongly induces CYP2C19 resulting to both an increase level of clopidogrel active metabolite and platelet inhibition, which in particular might potentiate the risk of bleeding. As a precaution, avoid concomitant use of strong CYP2C19 inducers

Concomitant use of strong inducers of CYP2C19 results in increased plasma concentration of the active metabolite of clopidogrel and an increase in platelet inhibition.

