9.2.6 PHARMACOKINETIC BLOOD SAMPLE COLLECTION

Blood samples (5 mL each) for PK analysis will be collected at pre-dose and at 0.25, 0.5, 0.75, 1, 1.5, 2, 3, 4, 6, 8, 12 and 24 h after study drug administration on Days 1 and 6 in each period. On Days 3, 4 and 5 in each period only the pre-dose sample will be collected.

The pre-dose (0.0 or 24.00 hour) blood sample shall be taken within 45 minutes prior to dosing on each dosing day in each period. All post-dose samples in each period will be collected within + 2 minutes of the scheduled time of blood sample collection.

Note:

In each period, 24 hour post dose sample of Day 1 will be considered as pre-dose sample of respective day.

PK blood samples will be collected through an indwelling intravenous cannula placed in a forearm vein or dorsal aspect of hand of the subjects. Intravenous indwelling cannula will be kept in situ as long as possible (up to 12 h) by injecting 0.3 mL of normal saline (to prevent cannula from clogging) and 0.3 mL of normal saline diluted blood will be discarded prior to collection of the next PK sample. In case the indwelling cannula is blocked or does not function properly or it must be removed for practical reasons, then if necessary re-cannulation procedures will be performed and particular blood sample may be collected by direct vein puncture. A blood sample of $(1 \times 3.0 \text{ mL})$ will be collected to perform Beta hCG test (for female subjects) at screening. Extra blood sample may be collected for repeat laboratory test(s), if required, at the discretion of the investigator.

Total volume of blood drawn will not exceed 551.4 mL+ 10 mL per male subject and 563.4 mL + 10 mL per female subject for the entire study.

Description	Blood loss for male subjects	Blood loss for female subjects
Blood withdrawn for screening	20	20
Blood loss for the samples of period I and II (for PK)	290	290

CONFIDENTIAL

Page 47 of 74

	Ipca Laboratories Ltd		
Study Protocol: CBCC/2019/003	Version 1.0 (Amendment 3.0))	Dated: 22/Apr/2021
Blood loss for the samples of period l Pharmacodynamic blood sample (Ag	`	135	135
Discarded blood of normal saline		14.4	14.4
Blood withdrawn for post study labor	atory assessment	12	12
Blood withdrawn for serum pregnanc subjects only)	y test (for female	-	12
Blood withdrawn for coagulation par- laboratory tests at housing of both per period I		80	80
Total blood loss for the study*		551.4	563.4

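### The vomiting rule in section 8.2 works on the whole period and, read naturally, discards a completed Day 1 loading-dose PK profile when the vomiting follows a later dose

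*Protocol*

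**What the plan says.** Note 2 of Protocol section 8.2 sets the rule for a subject who vomits within 2 hours of a dose: "the PK blood sampling for that period will be stopped and PK data will not be evaluated for PK". Pharmacodynamic (PD) assessments go on and the subject may enter later periods. The reason given is that "Vomiting early after administration of the test medication may decrease the bioavailability of the test drug". The note separates neither the loading dose from the maintenance doses nor one dosing day from another.

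Section 7.1 gives each period one loading dose and five daily maintenance doses. Section 9.2.6 schedules serial PK sampling up to "12 and 24 h after study drug administration on Days 1 and 6 in each period", and adds that "On Days 3, 4 and 5 in each period only the pre-dose sample will be collected". It also states: "In each period, 24 hour post dose sample of Day 1 will be considered as pre-dose sample of respective day". Pre-dose samples, including this one, are drawn within 45 minutes before dosing. Section 14.3 compares single-dose and multiple-dose exposure (Cmax, AUCt, AUCinf) as separate analyses, in line with the secondary objective in section 6.1. Section 14.4 plans a population PK-PD analysis of MP-H4. Sections 7.1 and 8.2 rule out replacing subjects who leave.

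**The concern.** The rule acts on the period, but the analysis uses the profile. A period-wide exclusion suits a design with one dose and one profile per period. Here a period has six occasions that can trigger the rule. On five of them, the Day 1 profile is already finished. The note's own reason, reduced bioavailability of the vomited dose, cannot reach back to a dose already followed for 24 hours.

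At stake are valid loading-dose data in two metabolizer groups of 20. A lost Day 1 profile also breaks that subject's within-subject comparison of AT-10 with clopidogrel. PD data are kept, so the subject can remain in the PD data set with no matching MP-H4 concentrations for the PK-PD analysis.

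**Working it through.** **Check of the schedule.** Section 9.2.6 lists one pre-dose and 12 post-dose samples on Days 1 and 6, and one pre-dose sample on each of Days 3, 4 and 5.

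- Samples per period: 13 + 3 + 13 = 29.
- Volume over both periods: 29 × 5 mL × 2 = 290 mL.

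This reproduces the 290 mL in the blood-loss table of section 9.2.6. The 24-hour sample of Day 1 is therefore also the Day 2 pre-dose sample, and the Day 1 profile closes before dose 2. An event on Days 2 to 6 leaves all 13 Day 1 samples untouched, which is 13/29 = 45% of the period's PK samples.

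**Size of the loss, as an illustration.** The protocol gives no vomiting rate. Let p be the assumed risk of vomiting within 2 hours of a dose, the same for every dose and independent between doses. There are 40 subjects × 2 periods = 80 Day 1 profiles.

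- Lost under the natural reading: 80 × [1 − (1 − p)^6].
- Lost if only the Day 1 dose counts: 80 × p.
- Lost although the Day 1 dose was retained: 80 × (1 − p) × [1 − (1 − p)^5].

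| p | Natural reading | Day 1 dose only | Lost although Day 1 unaffected |
|---|---|---|---|
| 0.5% | 2.4 | 0.4 | 2.0 |
| 1% | 4.7 | 0.8 | 3.9 |
| 2% | 9.1 | 1.6 | 7.5 |

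For p = 1%: 80 × 0.99 × (1 − 0.99^5) = 80 × 0.0485 = 3.9.

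**Day 1 crossover pairs.** A subject who completes both periods takes 12 doses. Under the natural reading the Day 1 pair is broken with probability 1 − (1 − p)^12. If only the two Day 1 doses count, it is 1 − (1 − p)^2. For p = 0.5%, 1% and 2% this gives 5.8%, 11.4% and 21.5%, against 1.0%, 2.0% and 4.0%. Per group of 20, that is 1.2, 2.3 and 4.3 pairs against 0.2, 0.4 and 0.8.

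**Day 6.** Section 5 gives a half-life of about 6 hours for clopidogrel after 75 mg, and says: "The half-life of the active metabolite is about 30 minutes". A Day 4 dose precedes the Day 6 dose by 48 hours, or 8 clopidogrel half-lives, so 0.5^8 = 0.4% remains. A Day 5 dose precedes it by 4 half-lives, so 0.5^4 = 6% remains. The protocol states no half-life for AT-10, which is one of the two analytes compared in section 14.3. The calculation cannot be completed for it.

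**The case against.** Several counter-arguments carry weight.

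**Scope.** The words limiting the rule to the period attach to the stopping of sampling. The clause on evaluation has no stated scope. A reader might infer that the protocol certainly voids the whole period's PK, but it could mean only data from the event onward. The whole period remains the natural reading, and under either one the note fails to say that a finished Day 1 profile is kept. Section 13 says all available samples will be analysed, but this concerns the assay and does not put data back into the PK evaluation. It does mean that Day 1 samples already drawn need not be lost for good, whereas samples never drawn cannot be recovered.

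**Size.** Nothing in the protocol anchors p at 0.5% to 2%. If vomiting recurs in the same subjects, fewer pairs are lost at a given rate per dose. The pair figures concern Day 1 profiles only. Pairs losing either profile under profile-level exclusion number 1 − (1 − p)^4, or 2.0%, 3.9% and 7.8%. That is a different question and does not alter the Day 1 contrast.

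**Day 6.** A reader might infer that a Day 6 profile after an earlier vomited dose is plainly valid. The documents do not show this without an AT-10 half-life. Treating Day 6 cautiously is a judgement, not an error.

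**PK-PD model.** The note excludes data from PK evaluation. It does not expressly bar concentrations already collected from the population analysis. Its sampling stop nevertheless removes later samples that the model would use.

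**Importance.** PK is a secondary objective, the sample size was not based on PK variability, and the study is declared not to be a bioequivalence study. The comparison of AT-10 between metabolizer types needs no within-subject pair. All of this lowers the impact.

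**Conclusion.** The point holds for the Day 1 profile. On its natural reading, Note 2 discards a complete loading-dose profile on five of six trigger occasions per period, for a reason that cannot apply to it. This conclusion rests only on the sampling schedule and needs no half-life or vomiting rate. The numerical size, about 2.0 to 7.5 of 80 Day 1 profiles lost needlessly, depends on an assumed risk of 0.5% to 2% per dose and on independence between doses. It is not a forecast. The documents support neither the claim that Day 6 is unaffected by earlier vomiting nor the claim that the sampling stop is wrong in itself. The impact is moderate to low, and the change is worth making because it costs little.

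**What to change.** Reword Note 2 of section 8.2 so that PK exclusion follows the affected profile:

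- Vomiting within the window after the Day 1 dose excludes the Day 1 profile.
- Vomiting within the window after the Day 6 dose excludes the Day 6 profile.
- A completed Day 1 profile is always kept after an event on Days 2 to 6.
- After an event on Days 2 to 5, any Day 6 profile that is collected is evaluated with a flag, and a sensitivity analysis leaves it out.

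The sponsor should also reconsider whether the period-wide stop of PK sampling is needed, given that PD blood draws continue and the population PK-PD analysis in section 14.4 needs matching concentrations. That decision is the sponsor's.

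The cost is a protocol rewording and one extra sensitivity analysis. No sample is added to the planned schedule.
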